15.1. Appendix 1: Referenced Study Documents, Software and Standards

Document, Software, or Standard	Version / Date
Protocol	Amendment V02 / 06 April 2023
Electronic Case Report Form (eCRF)	V3.0 30JUN2023
SAS® Software	9.4
National Cancer Institute-Common Terminology Criteria for Adverse Events (NCI-CTCAE)	5.0 / 27NOV2017
Medical Dictionary for Regulatory Activities (MedDRA®)	26 or higher / latest version at database lock (DBL)
World Health Organization Drug Dictionary (WHODrug)	B3 Global / latest version at DBL (March 2023 or later)
Response Evaluation Criteria in Solid Tumours (RECIST)	1.1 / 2009
Immune-Response Evaluation Criteria in Solid Tumors (iRECIST)	2017
Lugano classification	2014

15.2. Appendix 2: Descriptive Statistical Summaries

Descriptive Statistical Summaries
Numerical Data
Numerical variables will be summarized using descriptive statistics, displaying

 the number of subjects in the analysis group, the number of subjects with data, sample mean, sample standard deviation (calculated as the square root of an unbiased variance estimate), sample median, minimum (min) and maximum (max).
Categorical Data

 Categorical variables will be summarized by using frequency counts and percentages. The number of subjects with missing values will be displayed. Unless otherwise specified, the denominators used for calculating sample proportions will be the number of subjects in the analysis group (Subsection 6.2) of the specified statistical analysis set (or a subset of the statistical analysis set under use). For select ordinal categorical variables, cumulative counts and cumulative percentages may be presented, if appropriate.

15.3. Appendix 3: Data Display Conventions

Data Display Conventions	
Precision	
QMS Document Name: Statistical Analysis Plan Template(EN)	Page 34 of 41
QMS No (include version ref): STF-015-GL.03	Document date: 14JUL2022
CONFIDENTIAL	

Data Display Conventions

- Numeric data will be reported at the precision collected on the eCRF.
- The reported precision from non-eCRF sources will follow the same principles as described below but may be adjusted to a clinically interpretable number of decimal places (dp).
- Means and medians will be presented by 1 additional decimal place, and standard deviation will be presented by 2 additional decimal places than the standard presentation level of the respective data. Minimum and maximum values will be presented using the same number of decimal places as the original data. Standard errors and CI limits will be presented by 1 additional decimal place than corresponding point estimates.
- If not otherwise stated, percentages will be presented to 1 decimal place. However, if the percentage (or estimated proportion) is 100% exactly, no decimal place will be shown, whereas presented as 100.0% implies that the percentage is in the half-open interval [99.95%, 100.0%).
- Reasonable number of dps will be adjusted for proper presentation and interpretation. The maximum number of decimal places reported shall be 4 for any summary statistic, unless otherwise stated.

Default Presentation Precision

Name	Description	Decimal Place (dp)
N	Number of Subjects in the Treatment Group	Always 0 decimal.
n	Number of Subjects with Non-Missing Values	Always 0 decimal.
%	Percentage	1 decimal for categorical data
Mean	Arithmetical Mean	1 more decimal than original data
StdDev	Standard Deviation	2 more decimal than original data
Median	Median	1 more decimal than original data
Min.	Minimum	Same as original data
Max.	Maximum	Same as original data
SE	Standard Error	1 more decimal than the corresponding point estimate
CI	Confidence Interval	1 more decimal than the corresponding point estimate
P value	P value	3 significant digits

Rounding Rules

- In general, explicit rounding will only occur when presenting data but not when analyzing data. Thus, data in recorded in the Analysis Data Sets (e.g., ADaM data sets) will not be rounded.
- By default, presented data will be rounded to the nearest required presentation precision, with a “round ties to even” tie-breaking rule according to IEEE 754-2019.
- When presenting CIs, the lower interval limit will always be rounded down and the upper interval limit will always be rounded up in order preserve the claimed (exact or asymptotic) confidence level. When either limit is outside of the parameter space (e.g., below 0 or above 1 for proportions), the interval will be truncated at the boundary of the parameter space.

Zero Count Presentation

- For descriptive summaries, if the number of subjects in a category is 0, then percentage will not be displayed, and only a count of 0 will be shown.
- However, structural zeros (e.g., when the count is deemed to be 0 before obtaining actual data), missing data or inapplicable/unevaluable summaries will be presented as –, NA or NE (not applicable or not evaluable, respectively).

Data Display Conventions	
Sorting in Displays	

 ● In data listings, data records will be sorted by study phase (escalation vs expansion), therapy (monotherapy vs combination therapy), dose level / arm, site, and subject, and when appropriate by visit, scheduled time point or other identifiers for sequence or type of observation. ● In descriptive summaries involving categorical variables only, e.g., summaries of 
 • medical history by SOC and PT, • medications by ATC category and PN, and • adverse events by SOC and PT, the categories and sub-categories will be presented by decreasing frequency using sorting variables in the following preference order: 
 1. Total count (irrespective of whether the total column is shown or not) 2. Count from higher dose level for escalation part or from higher arm code for expansion part (D > C > B > A) 3. Alphabetical order of the category label 
Sorting variables with lower preference will only be used if ties remain using sorting variables with higher preference.
	

15.4. Appendix 4: Study Day, Duration, Period, Visit and Analysis Windows

Study Day, Duration, Period, Visit and Analysis Windows
Study Day
For each study subject, Day 1 is defined as the date corresponding to the first administration of any study drug. Study days after Day 1 are calculated as the number of days from Day 1:

 ● Study Day = Date of interest – Date of Day 1 + 1, if the date of interest is on or after date of Day 1; ● Study Day = Assessment date – Date of Day 1, if the assessment date is prior to Day 1. ● Study Day is set to missing if the date of interest is missing.
Time Unit and Duration

 ● Unless otherwise specified, day is the primary time unit for derived time and duration. ● Derived time units include 
 1. Week = 7 days 2. Month = 30.4375 days, 3. (Gregorian) Year = 365.25 days = 12 months. 
Thus, 1 month and 4 weeks are considered different.
 ● Unless otherwise specified, duration of time is defined from the starting day through the ending day, inclusive of both boundary days.
Study Periods

 ● Screening period: beginning on the day of informed consent, or Study Day –28, whichever is latest, and ending on Day –1

QMS Document Name: Statistical Analysis Plan Template(EN)	Page 36 of 41
QMS No (include version ref): STF-015-GL.03	Document date: 14JUL2022
CONFIDENTIAL	

Study Day, Duration, Period, Visit and Analysis Windows

- Treatment period: beginning on Study Day 1 and ending on the last day of the End of Treatment (EoT) visit. In case that the EoT visit is missed for any reason, the treatment period will end on the 28th day since the last dose of any study drug.
- Safety follow-up period: 30-day safety follow-up period since the first day after the treatment period and or study discontinuation date, whichever occurs first.
- Unless otherwise specified, events in the screening period are considered as pre-treatment, events in the treatment period and safety follow-up period are considered as on-treatment.

Time Points and Assessment Windows

- Subject visits will be presented according to the nominal visit and/or time points as obtained on the eCRF.
- Unscheduled visits will be included in subject data listing but will not be presented in descriptive summary tables, except for deriving time to event (TTE) variables or otherwise specified.

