1.2. Study Objectives and Endpoints

Objectives	Outcome Variables
Primary Objectives and Endpoints for Dose Escalation	

 To determine the MTD and/or recommended dose for expansion (RDE). 	
 Frequency, severity, and relatedness of treatment-emergent adverse events (TEAEs) and serious adverse events (SAEs), changes in safety laboratory parameters, and DLTs (if observed) for WTX- 330.
Dose Escalation and Expansion (Parts 1 and 2)	

 To further characterize the safety of WTX- 330 	
 Frequency, severity, and relatedness of TEAEs and SAEs, changes in safety laboratory parameters, and DLTs (if observed) for WTX-330

 To evaluate the anti-tumor activity of WTX-330 	
 Overall response rate (ORR) (complete response [CR] + partial response [PR]), duration of response (DOR) by Response Evaluation Criteria in Solid Tumors (RECIST) 1.1 and immune-overall response rate (iORR) (immune-complete response [iCR] + immune-partial response [iPR]) by immune-RECIST (iRECIST), or response by Lugano criteria (for lymphoma only)
Secondary Objectives and Endpoints (Parts 1 and 2)	
	
	

 To evaluate the immunogenicity of WTX330 	
 Incidence and titers of ADAs towards WTX-330

QMS Document Name: Statistical Analysis Plan Template(EN)	Page 6 of 41
QMS No (include version ref): STF-015-GL.03	Document date: 14JUL2022
CONFIDENTIAL	

Objectives	Outcome Variables
Secondary Objectives and Endpoints (Parts 2)	

 To evaluate the antitumor activity of WTX-330 in patients with relapsed/refractory (r/r) advanced or metastatic malignancies who have progressed on CPIs or who have tumor indications for which CPIs are not approved 	
 ORR (CR + PR) based on best overall response (BOR) DOR Disease control rate at month 3, 6 and 9 Progression free survival (PFS) per RECIST v1.1 (solid tumor) and iRECIST or Lugano classification (lymphoma; Cheson et al., 2014) assessed by Investigator. Overall survival (OS)
Exploratory Objectives and Endpoints (Parts 1 and 2)	

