- Quantitative laboratory data will be summarized using descriptive statistics (Subsection 15.2) of actual values and changes from baseline to each visit over time.
- Shift of the worst post-baseline CTCAE grade from baseline will be summarized as well.

Some tests (including red blood cells (RBC) count, hematocrit, Chloride, lactic acid dehydrogenase, prothrombin time, etc) with normal range and are not CTCAE gradable. The shift of these tests from baseline low/normal/high to lowest/highest post-baseline will be prepared.

The number and percentage of patients with elevated AST, ALT, total bilirubin, and alkaline phosphatase will be summarized for safety analysis set. Elevations will be summarized as a function of the ULN.

- $3 \times \text{ULN}$, $5 \times \text{ULN}$, $10 \times \text{ULN}$, and $20 \times \text{ULN}$ elevations of AST, ALT, and either ALT or AST.
- $>1.5 \times \text{ULN}$ and $>2 \times \text{ULN}$ elevations of Total bilirubin.
- Any elevations of ALP $>1.5 \times \text{ULN}$.
- Elevation of ALT/AST ($>3 \times \text{ULN}$) accompanied by Total bilirubin ($>1.5 \times \text{ULN}$, $>2 \times \text{ULN}$).

A separate listing will also be provided for all hematology, coagulation, clinical chemistry (including thyroid function tests) and urinalysis. Laboratory values that are outside the normal range will also be flagged in the data listings, along with corresponding normal ranges. Any out-of-range values that are identified by the investigator as being clinically significant will also be shown in the data listing.

For all NCI-CTCAE programmatically gradable laboratory tests, separate listings will be provided for all Grade 3 or higher abnormal lab results (in either direction) together with corresponding baseline results.

9.6. **Electrocardiograms (ECG)**

For triplicate ECG measurements, the mean of all assessments at each scheduled time point will be used for descriptive summarization purpose; however, all ECG measurements will be provided in data listings.

Local-read ECG data will be listed overall and a separate listing for any clinically significant finding in ECG values will be provided.

Absolute and CFB values for PR Interval, QT Interval, QTcF, QRS Duration and HR will be summarized descriptively by visit and by dose level in escalation phase and by arm in expansion phase. QTcF will be calculated with $\text{QT}/(\text{RR})^{1/3}$.

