The frequency and percentage of subjects will be tabulated descriptively for the following:

- Highest post-baseline QTcF >450 msec
- Highest post-baseline QTcF >480 msec
- Highest post-baseline QTcF >500 msec
- Maximum CFB of QTcF > 30 msec
- Maximum CFB of QTcF > 60 msec

9.7. **Vital Signs and Body Measurements**

The absolute values of vital sign and body measurements (including weight, systolic blood pressure, diastolic blood pressure, HR, and temperature) and the CFB measurements will be summarized descriptively for each analysis group over scheduled time points (visits) as defined in Subsection 6.2.

QMS Document Name: Statistical Analysis Plan Template(EN)	Page 26 of 41
QMS No (include version ref): STF-015-GL.03	Document date: 14JUL2022
CONFIDENTIAL	

The number and percentage of patients with the following notably abnormal vital signs and body measurements will be presented by visit:

- Clinically notable elevated values:
 - Systolic BP: ≥ 180 mmHg and an increase ≥ 20 mmHg from baseline
 - Diastolic BP: ≥ 105 mmHg and an increase ≥ 15 mmHg from baseline
 - Weight: Increase of $\geq 10\%$ from baseline
 - Heart rate: ≥ 120 bpm with an increase of ≥ 15 bpm from baseline
 - Temperature: $> 38^\circ\text{C}$
- Clinically notable decrease values:
 - Systolic BP: ≤ 90 mmHg and a decrease ≥ 20 mmHg from baseline
 - Diastolic BP: ≤ 50 mmHg and a decrease ≥ 15 mmHg from baseline
 - Weight: decrease of $\geq 10\%$ from baseline
 - Heart rate: ≤ 50 bpm and a decrease ≥ 15 bpm from baseline
 - Temperature: $< 35^\circ\text{C}$

Vital signs will be provided in a data listing by subject using the Safety Analysis Set.

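### Read literally, SAP 15.4 keeps unscheduled values out of the worst-value laboratory, liver and QTcF tables, so those tables could understate toxicity

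*SAP*

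**What the plan says.** The general rule is in SAP 15.4, under Time Points and Assessment Windows. Unscheduled visits go into the subject listings but "will not be presented in descriptive summary tables, except for deriving time to event (TTE) variables or otherwise specified". The rule therefore has two exceptions: time-to-event derivations, and anything specified elsewhere.

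Several safety tables are built on one extreme value per subject, or on whether a threshold was ever crossed:

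- **CTCAE-graded laboratory tests (SAP 9.5):** "Shift of the worst post-baseline CTCAE grade from baseline will be summarized as well". Shells 14.3.7.1.3/4, 14.3.7.2.3/4 and 14.3.7.3.3/4.
- **Tests without a CTCAE grade (SAP 9.5):** "The shift of these tests from baseline low/normal/high to lowest/highest post-baseline will be prepared". Shells 14.3.7.1.5/6, 14.3.7.2.5/6 and 14.3.7.3.5/6.
- **Liver tests (SAP 9.5):** "The number and percentage of patients with elevated AST, ALT, total bilirubin, and alkaline phosphatase will be summarized for safety analysis set", by multiples of the ULN and with a combined ALT/AST plus bilirubin count. Shells 14.3.7.2.7/8.
- **QTcF (SAP 9.6):** categories such as "Highest post-baseline QTcF >500 msec", and the largest change from baseline. Shells 14.3.9.3/4.

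None of these sections or shells says whether unscheduled values count. For triplicate ECGs, SAP 9.6 bases the descriptive summaries on the mean at each scheduled time point.

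**The concern.** Leaving unscheduled visits out of by-visit means is normal and sensible, because such visits have no common time point. A worst-value table asks a different question: how bad did it get for this subject at any time after the first dose? An extra blood draw or ECG is one of the places where that worst value may lie, for example when a result is repeated because it was abnormal. If such values are dropped, the table no longer answers its own question.

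This matters because changes in safety laboratory parameters are among the outcome variables for the primary safety objectives (SAP 1.2). The liver and QTcF threshold tables are also ones that readers use to judge a dose. A subject whose ALT passed 5 times ULN, or whose QTcF passed 500 msec, only at an unscheduled visit would not be counted in the table meant to show it.

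**Working it through.** The plan gives no figure that depends on this rule, so there is nothing to reproduce. The check is mainly a comparison of texts.

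1. **Does the rule reach derived values, or only visit rows?** It makes an exception for deriving time-to-event variables. Those variables have no visit rows. The exception is needed only if the rule also governs which values enter a derivation. Worst grade, highest QTcF and largest change are derivations too, and they are not excepted. SAP 9.6 also calls the QTcF counts a descriptive tabulation, which places them within the rule's scope.

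2. **Is anything otherwise specified for these tables?** No override appears in SAP 9.5, SAP 9.6 or the shells listed above. Elsewhere the SAP names the wider data when it wants them. Best overall response per RECIST 1.1 draws on all visits (SAP 8.2.2), and antibody sampling includes unscheduled visits (SAP 11). The silence in the safety sections therefore leaves the default in force.

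3. **Do table and listing agree?** Listing 16.2.8.2.2 shows all visits of a subject who reaches 3 times ULN for AST or ALT, or 1.5 times ULN for bilirubin, and SAP 15.4 keeps unscheduled records in listings. A subject whose only ALT above 5 times ULN was unscheduled would appear in that listing but, on the literal rule, would not be counted in Table 14.3.7.2.7. The shells do expect unscheduled records: sample rows for them appear in Listings 16.4.6.2 and 16.4.6.4.

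4. **Direction.** Let S be a subject's scheduled post-baseline values and U the unscheduled ones. Then max(S) ≤ max(S and U), and the lowest value behaves in mirror image. Excluding U can never make the worst value worse.

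5. **Scale of one missed subject.** SAP 3.1 plans 3 to 6 patients per dose group: 1/3 = 33% and 1/6 = 17%. SAP 3.2 plans up to 20 per expansion arm: 1/20 = 5%.

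6. **Sensitivity, on assumed inputs only.** Let p be the true share of subjects crossing a threshold, and f the share of those whose only qualifying value is unscheduled. The documents give neither. The expected count is n·p·(1−f), and the chance that the table shows at least one such subject is 1 − [1 − p(1−f)]^n. For n = 6 and p = 20%:

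| f (assumed) | Expected count | Chance of showing at least one |
|---|---|---|
| 0 | 6 × 0.20 = 1.20 | 73.8% |
| 10% | 6 × 0.18 = 1.08 | 69.6% |
| 25% | 6 × 0.15 = 0.90 | 62.3% |
| 50% | 6 × 0.10 = 0.60 | 46.9% |

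For n = 20 and the same p, the expected count falls from 4.0 to 3.6, 3.0 and 2.0. These rows show how the effect would scale. They do not estimate it, and f could be zero.

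**The case against.** The strongest reply is that the rule concerns layout. It follows a sentence about presenting visits by their nominal label. SAP 9.5 separates values at each visit from the worst post-baseline grade, and shell 14.3.9.3 separates the highest post-baseline QTcF from the rows for individual time points. Words such as worst and highest carry no limit to scheduled visits, and neither does the baseline definition in SAP 15.5. This reading is possible, and some programmers would adopt it. It is the weaker one, because it leaves the time-to-event exception without a purpose and sits poorly with the scheduled-time-point wording for ECGs. If the text is only ambiguous, two programmers could still produce different tables from the same data.

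The reply stands against three stronger inferences that a reader might draw:

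- **That unscheduled data are barred from every summary except time-to-event.** The rule also yields wherever something else is specified, and RECIST best overall response already uses all visits.
- **That a missed abnormality would be visible only in listings.** Treatment-emergent events are defined by date relative to dosing (SAP 9.3.1.3). Hy's Law or Grade 3 or higher ALT/AST is an event of special interest (SAP 9.3.1.4) with its own tables, 14.3.2.12.1/2. An unscheduled abnormality reported as an adverse event is therefore tabulated. QTcF has no such special-interest category and relies on ordinary adverse event reporting.
- **That dose finding is biased.** The MTD rests on DLTs in the dose-determining set, and the Dose Escalation Committee reviews all available data, not these end-of-study tables.

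**Conclusion.** The concern holds as a defect in a data-handling rule. Taken literally, SAP 15.4 excludes unscheduled values from the worst-grade, lowest/highest, liver-threshold and QTcF-extreme tables, and nothing in SAP 9.5, SAP 9.6 or the shells lifts the exclusion. Any resulting error can only make the profile look milder.

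The documents do not support saying that toxicity will be understated, or by how much. That depends on how often a subject's worst value is unscheduled, which they do not report. The one-subject figures (17 to 33 percentage points in a cohort of 6 down to 3, and 5 points in an arm of 20) assume that a miss has occurred. The effect is confined to the listed tables. By-visit summaries are rightly limited to scheduled visits and are not part of this point. It should be corrected, but it casts no doubt on the dose-finding analysis.

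**What to change.** - **SAP 15.4:** limit the exclusion to by-visit summaries. State that worst, lowest, highest, maximum-change and threshold summaries of laboratory tests, liver tests and QTcF use all post-baseline values, scheduled and unscheduled.
- **SAP 9.5 and 9.6:** repeat the statement. In 9.6, confine the scheduled-time-point wording for triplicate ECG means to the by-visit summaries, and say how an unscheduled ECG enters the extremes.
- **Shells:** add a note to 14.3.7.1.3 to 14.3.7.1.6, 14.3.7.2.3 to 14.3.7.2.8, 14.3.7.3.3 to 14.3.7.3.6, and 14.3.9.3/4. In 14.3.9.3/4 the note should cover only the highest-value and largest-change rows.
- **Vital signs:** do not extend the rule to notable vital signs until SAP 9.7, which presents them by visit, is reconciled with shell 14.3.8.3, which does not.

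The cost is a few sentences and a little programming. The values are already destined for the listings, so no new data are needed. Reported rates may look slightly less favourable.

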15.5. Appendix 5: Derived Data And Definitions

Derived Data And Definitions

Baseline & Change From Baseline

- The baseline is defined to be the last non-missing value prior to the first WTX-330 dose.
 - For assessments performed on Day 1, if the time of the day is missing but scheduled time point is recorded as pre-dose, the assessment may be considered the baseline assessment for the respective study procedures.
- Change from Baseline (CFB) = Post-baseline Assessment – Baseline Assessment.
 - CFB will be set to missing if corresponding post-baseline assessment or the baseline assessment is missing
- Percent CFB = $100 \times (CFB / \text{Baseline Assessment}) \%$, with the following exceptions:
 - If both CFB and baseline assessment are 0, the corresponding percent CFB will be set to 0.
 - If baseline assessment is 0 or missing but the CFB is non-zero, the percent CFB will be set to missing.

Age

Age at informed consent will be calculated from the date of birth to the date of informed consent.

Prior and Concomitant Medications, Procedures, and Medical Conditions

- Prior medications – all medications that ended before Day 1.
- Concomitant medications – all non-study drug medications used on/after day 1.
- Prior and concomitant procedures are defined analogously.

QMS Document Name: Statistical Analysis Plan Template(EN)	Page 37 of 41
QMS No (include version ref): STF-015-GL.03	Document date: 14JUL2022
CONFIDENTIAL	

Derived Data And Definitions

- If the start and/or end dates are partially recorded or missing completely, refer to Subsection 15.6 for the determination of prior vs concomitant status.

15.6. Appendix 6: Premature Withdrawals & Handling of Missing Data**Premature Withdrawals & Handling of Missing Data****Premature Withdrawals**

During the dose escalation phase, if a subject in Cycle 1 discontinues, holds, or modifies WTX-330 dose for a reason other than a DLT as reviewed by DEC and is not followed for safety for a minimum of 28 days, the subject may be replaced.

For the Dose Expansion Phase, subjects will be replaced if they do not have at least one post-baseline efficacy assessment and did not discontinue due to clinical progression.

Handling of Missing or Partial Dates

In the presence of missing or partial dates, the determination of “prior” and “concomitant” status for non-study drug medications, and TEAE will follow the rules below:

Partial start date for Adverse Event, partial start date for Medications, and partial date of diagnosis

- if month and day are missing, and the year is the same as the year of first WTX-330 dose, then assign the date of first WTX-330 dose as start date; else assign Jan 1st of the year.
- if only the day is missing, and the month and year are same as the month and year of first WTX-330 dose, then assign the date of first WTX-330 dose as AE start date; else assign 1st day of the month.
- Compare the imputed date with the date of last known alive/contact; if the imputed date is later than the date of last known alive/contact, then assign the date of last known alive/contact as AE start date.

Partial end date for Adverse Event, and partial end date for Medications:

- Assign DEC 31st of the year if both Month and Day are missing.
- Assign last day of the month if only Day is missing.
- Assign ‘ongoing’ if Year, Month and Day are missing.
- Compare the imputed date with the date of last known alive/contact; if the imputed date is later than the date of last known alive/contact, then assign the date of last known alive/contact as AE end date.

The data listings will report original data instead of the imputed date. The imputed date will be used to categorized TEAE, Prior/Concomitant Medication.

QMS Document Name: Statistical Analysis Plan Template(EN)	Page 38 of 41
QMS No (include version ref): STF-015-GL.03	Document date: 14JUL2022
CONFIDENTIAL	

